### **5.2.2 Pralatrexate**

In Arm A, pralatrexate will be administered at the entry dose of  $30 \text{ mg/m}^2$  day 1, 8, 15 Q4W which represents the MTD identified in the PROPEL trial. Allocation of participants to doses of Pralatrexate will be conducted according to the study design described in [Section 10: Statistical Considerations](#).

In Arm B, pralatrexate will be administered at the entry dose of  $20 \text{ mg/m}^2$  day 1, 8, 15 Q4W and subsequently de-escalated (if applicable) following the study design described in the Statistical Considerations.

All patients receiving pralatrexate will receive folic acid at the dose of 1,000 mg orally daily and vitamin B12 intramuscularly every 2 cycles (8 weeks) as recommended in the package insert of the product. The vitamin supplementation will start prior to the first dose of pralatrexate as recommended in the drug package insert. Leucovorin will be used to decrease the risk of mucositis in all patients receiving treatment with pralatrexate. Leucovorin will be given at the dose of 15 mg orally twice daily and should be held the day before, the day of and the day after pralatrexate treatment. Leucovorin is mandatory for patients on trial.

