## 6.2 Trial Treatments

The treatment arms to be used in this trial are outlined in Table 7, Table 8 and Table 9 below.

Table 7: Trial Treatment – Arm A

Agent	Premedication Precautions	Dose	Route	Schedule A	Cycle Length
Pembrolizumab	N/A	200 mg (flat dose)	IV Administered first during cycle 1	Days 1*	Q3W
Pralatrexate	B12 and Folate supplementation (to be started within one week before initiation of treatment), and leucovorin (LV) as outlined	20 or 30 mg/m  **	IV push	Days 1, 8, 15	Q4W

\*Day 1 for pembrolizumab administration refers only to cycle 1 of treatment. Pembrolizumab will be continued every 3 weeks following the first administration.

\*\* Doses as appropriate for assigned dose level. Pralatrexate dose will be calculated using weight at cycle 1 day 1, unless weight has changed more than 10%. If so, the total dose should be calculated on the updated weight.

Table 8: Trial Treatment – Arm B

Agent	Premedication Precautions	Dose	Route	Schedule B	Cycle Length
Decitabine	Antiemetic	10 mg/m  *	IV	Days 1, 2,3,4,5	Q4W
Pralatrexate	B12 and Folate supplementation (to be started within one week before initiation of treatment) and leucovorin (LV)	20 mg/m  *	IV push	Days 1,8,15	
Pembrolizumab	N/A	200 mg (Flat dose)	IV	Day 8**	Q3W

\* Doses as appropriate for assigned dose level. Pralatrexate and decitabine dose will be calculated using weight at cycle 1 day 1, unless weight has changed more than 10%. If so, the total dose should be calculated on the updated weight.

\*\*Day 8 for pembrolizumab administration refers only to cycle 1 of treatment. Pembrolizumab will be continued every 3 weeks following the first administration.

Table 9: Trial Treatment – Arm C

Agent	Premedication Precautions	Dose	Route	Schedule C	Cycle Length
Pembrolizumab	N/A	200 mg (flat dose)	IV (Administered first during cycle 1)	Days 8*	Q3W
Decitabine	Antiemetic	20 mg/m  **	IV	Days 1,2, 3, 4, 5	Q4W

*\*Day 8 for pembrolizumab administration refer only to cycle 1 of treatment. Pembrolizumab will be continued every 3 weeks following the first administration.*

*\*\*Doses as appropriate for assigned dose level. Decitabine dose will be calculated using weight at cycle 1 day 1, unless weight has changed more than 10%. If so, the total dose should be calculated on the updated weight.*

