All patients receiving pralatrexate will receive folic acid at the dose of 1,000 mg orally daily and vitamin B12 intramuscularly every 2 cycles (8 weeks) as recommended in the package insert of the product. The vitamin supplementation will start prior to the first dose of pralatrexate as recommended in the drug package insert. If leucovorin is being used for rescue, this should be used at the dose of 15 mg orally twice daily and should be held the day before, of and after pralatrexate.

Trial treatment should begin on the day of randomization or as close as possible to the date on which treatment is allocated/assigned.

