### 7.3.2 Pralatrexate

Patient treated with pralatrexate are at risk of developing mucositis. The risk of developing mucositis can be lowered by pretreating patient with leucovorin 15 mg PO BID that has to be held the day before, day of and day after pralatrexate administration. The treatment with leucovorin will be given with treatment as noted above but can be given at the treating physician's discretion for pralatrexate related mucositis (i.e. in schedule delays). Pralatrexate and decitabine can induce hematologic toxicity that should be address with Neupogen/Neulasta support at the treating physician's discretion and as suggested in Table 12 and Table 13.

Doses may be omitted or reduced based on patient tolerance. Omitted doses will not be made up for at the end of the cycle; once a dose reduction occurs for toxicity, there will be no re-escalation. For dose modifications and omissions, use the suggested guidelines in Table 11, Table 12 and Table 13 below.

Table 11: Suggested Guidelines for Pralatrexate Dose Modifications for Mucositis after Cycle 1

Mucositis Grade a on the Day of Treatment	Action	Dose upon recovery to Grade ≤ 1
Grade 2	Omit dose	Maintain dose level
Grade 2 recurrence	Omit dose	Reduce to one dose level below
Grade 3	Omit dose	Reduce to one dose level below
Grade 4	Stop therapy	No further treatment with pralatrexate

a Per NCI CTCAE, Version 3.0

Table 12: Suggested Guidelines for Pralatrexate Dose Modifications for Hematologic Toxicities

Blood Counts on the Day of Treatment	Duration of Toxicity	Action	Dose upon re-start
Platelets < 50,000/µL	1 week	Omit dose	Continue prior dose
	2 weeks	Omit dose	Reduce to one dose level below
	>2 weeks	Stop therapy	No further pralatrexate
ANC 500-1,000/µL and no fever	1 week	Omit dose	Continue prior dose
ANC 500-1,000/µL with fever (a single temperature of > 38.3°C or sustained temperature of ≥ 38°C for over one hour) or ANC <500/µL	1 week	Omit dose, give G-CSF or GM-CSF	Continue prior dose with G-CSF or GM-CSF support
	2 weeks or recurrence	Omit dose, give G-CSF or GM-CSF	Reduce to one dose level below with G-CSF or GM-CSF support
	>2 weeks or 2nd recurrence	Stop therapy	No further pralatrexate

Table 13: Suggested Guidelines for Pralatrexate Dose Modifications for All Other Treatment Related Toxicities

Toxicity Grade a on the Day of Treatment	Action	Dose upon recovery to Grade ≤ 2
Grade 3	Omit dose	Reduce to one dose level below

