## 7.8 Rescue Medications & Supportive Care

### 7.8.1 Prophylactic Measurements and Supportive Care

Patients will be permitted to receive appropriate supportive care measures as deemed necessary by the treating physician including but not limited to the items outlined below:

- **Diarrhea:** Diarrhea should be treated promptly as it could represent an immune-related adverse event due to pembrolizumab administration. Please follow section 7.8.2 for supportive care guidelines for immune-related adverse events in case of diarrhea.
- **Nausea/vomiting:** Nausea and vomiting should be treated aggressively, with agents such as prochlorperazine, metoclopramide, 5-HT-3 inhibitors, or benzodiazepines. Patients should be strongly encouraged to maintain liberal oral fluid intake during therapy, especially during the initial 14 days of each treatment cycle.
- **Fatigue:** May be cumulative with increasing cycles of therapy. Can be treated as recommended in the NCCN Guidelines 2017 available online.
- **Anemia:** Transfusions or erythropoietin may be utilized as clinically indicated for the treatment of symptomatic anemia but should be clearly noted as concurrent medications.
- **Thrombocytopenia:** Transfusion of platelets may be used if clinically indicated. Dose modification for thrombocytopenia is allowed. Prophylactic folic acid and vitamin B12 supplements may be necessary to reduce hematologic toxicity as indicated in section and should be used as detailed in section 5.2.2.
- **Neutropenia:** Prophylactic use of colony-stimulating factors including granulocyte colony stimulating factor (G-CSF), pegylated G-CSF or granulocyte-macrophage colony stimulating factor (GM-CSF) may be utilized if clinically indicated and as suggested in Table 12 and Table 13.
- **Hypokalemia or hypomagnesemia** should be corrected prior to administration of study drugs, and consideration should be given to monitoring potassium and magnesium in patients experiencing side effects potentially affecting serum electrolytes (e.g. patients with nausea, vomiting, diarrhea, fluid imbalance or cardiac symptoms.)
- **Oral Mucositis:** Pralatrexate may cause mucositis, including stomatitis or mucosal inflammation of gastrointestinal and genitourinary tracts; prophylactic folic acid and vitamin B12 supplements are necessary to reduce treatment-related mucositis; dosage modification may be required. Please see section 5.2.2 and the FDA approved package insert for any clarification.

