$$L_m(\theta_m) = \prod_{i \in \{1, 2, 3, 5, 8\}} \left( p_{mi}^{\exp(\theta_m)} \right)^{y_i} \left( 1 - p_{mi}^{\exp(\theta_m)} \right)^{n_i - y_i},$$

$y_i$  = the number of DLTs, and  $n_i$  = the number of treated patients in combination  $i$ . The ordering  $h$  with the largest likelihood is chosen and, within this ordering, DLT probability estimates are updated for each combination. If there is a tie between the likelihood values of two or more orderings, then the selected ordering  $h$  is randomly chosen from among the tied orderings. After accrual of each patient cohort into the trial, the DLT probability estimates,  $\tilde{R}(d_i)$ , are updated via

$$\tilde{R}(d_i) = p_{hi}^{\exp(\tilde{\theta}_h)}; \quad \tilde{\theta}_h = \arg \max L_h(\theta_h).$$

The DLT probability estimates are used to sequentially allocate participants according to the following rules:

1. If the most recent participant accrued to the study **does not** experience a DLT, then the recommended combination for the next participant will be the combination indicated by the model to have an estimated DLT rate closest to 25%. Escalation of both agents simultaneously or escalation of more than one dose level of either agent is not allowed.
2. If the most recent participant accrued to the study **does** experience a DLT:
  - a. If the DLT is mucositis or thrombocytopenia or mucositis plus neutropenia and/or thrombocytopenia, then the recommended combination for the next participant will be restricted to either the current combination administered to the most recent participant or to de-escalation of one dose level of Pralatrexate, based on which combination has an estimated DLT rate closest to 25%.
  - b. If the DLT is neutropenia or neutropenia and thrombocytopenia, then the recommended combination for the next participant will be restricted to either the current combination administered to the most recent participant or to de-escalation of one dose level of Decitabine, based on which combination has an estimated DLT rate closest to 25%

The study will sequentially repeat the estimation procedure after the enrollment and follow-up of each cohort. The allocation procedure will be repeated until sufficient information about the MTD has been obtained according to the stopping rules described below.

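### Leucovorin is mandatory prophylaxis in section 5.2.2 but conditional on rescue use in the text of section 6.2, so sites could differ on a co-medication that bears on a pralatrexate DLT

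*Protocol*

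**What the plan says.** Section 5.2.2 gives leucovorin a prophylactic purpose and full coverage: "Leucovorin will be used to decrease the risk of mucositis in all patients receiving treatment with pralatrexate". It sets 15 mg orally twice daily, withheld on the day before, the day of and the day after pralatrexate, and closes with "Leucovorin is mandatory for patients on trial".

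Section 6.2 handles leucovorin twice. The premedication column of Table 7 (Arm A) reads "B12 and Folate supplementation (to be started within one week before initiation of treatment), and leucovorin (LV) as outlined", and Table 8 (Arm B) lists leucovorin beside the vitamins in the same way. The paragraph below the tables repeats the vitamin instructions of 5.2.2, but where 5.2.2 has its mandatory leucovorin instruction it has "If leucovorin is being used for rescue, this should be used at the dose of 15 mg orally twice daily", followed by the same three hold days.

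Section 5.3 counts non-hematologic toxicity of grade 3 or higher as a DLT, and mucositis is not among the exceptions. Only DLTs before cycle 2 drive dose decisions. In section 10.2, Arm B rule 2a begins "If the DLT is mucositis or thrombocytopenia or mucositis plus neutropenia and/or thrombocytopenia" and then restricts the next participant to the current combination or one pralatrexate level lower.

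**The concern.** The same regimen is universal prophylaxis in one place and something used if rescue is needed in another. Section 6.2 also disagrees with itself, since its tables list leucovorin as premedication and its text makes it conditional. Table 7 refers to leucovorin as outlined without saying where, and the nearest outline is the conditional sentence.

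This is more than an editorial matter because the protocol itself says that leucovorin lowers the risk of mucositis. Severe mucositis in cycle 1 enters the DLT count from which the MTD is estimated. If sites in this multicenter trial read the rule differently, participants with and without prophylaxis would contribute to one likelihood, and the report could not say with which co-medication the recommended dose was tolerated.

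**Working it through.** **Texts side by side**

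| Place | Who | Status | Dose and holds |
|---|---|---|---|
| 5.2.2 | all on pralatrexate | mandatory prophylaxis | 15 mg twice daily; hold day before, of, after |
| 6.2, Tables 7-8 | Arms A and B | premedication, no condition | not given |
| 6.2, text | not stated | conditional on rescue use | same as 5.2.2 |

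Because dose and holds are identical, the 6.2 sentence does not describe a distinct rescue regimen. It changes only the status.

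**Sensitivity of allocation to one DLT: inputs**

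- Target DLT rate 25%, cohorts of one (10.1).
- Arm A: skeleton 0.08/0.15/0.25 for Levels -2/-1/1 (10.2); 1 DLT in 5 at Level 1 so far (10.1).
- Arm B: skeleton 0.25 for Combination 8 in all five orderings; for Combination 5 it is 0.11 (orderings 1 and 5) or 0.174 (orderings 2, 3 and 4) (10.2). So far 1 DLT in 4 at Combination 8 (10.1).

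The model is (skeleton)^exp(a), fitted by maximum likelihood. While all data sit at a level with skeleton 0.25, the estimate there equals y/n. Hence exp(a) = ln(y/n)/ln(0.25), and every other estimate is its skeleton raised to that power.

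**Arm A**

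| DLTs | exp(a) | Level -2 | Level -1 | Level 1 | Closest to 0.25 |
|---|---|---|---|---|---|
| 1/5 (current) | 1.161 | 0.053 | 0.111 | 0.200 | Level 1, as the plan states |
| 1/6 | 1.292 | 0.038 | 0.086 | 0.167 | Level 1 |
| 2/6 | 0.792 | 0.135 | 0.222 | 0.333 | Level -1 |

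At 2/6 the distances from 0.25 are 0.115, 0.028 and 0.083, so the next participant goes to Level -1.

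**Arm B**

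- Current, 1/4: exp(a) = 1, Combination 8 estimated at 0.25. Combination 8, as the plan states.
- No further DLT, 1/5: Combination 8 at 0.200, every other combination lower. Combination 8 continues.
- One mucositis DLT, 2/5: exp(a) = 0.661. Combination 8 is at 0.400 (distance 0.150). Combination 5, one pralatrexate level lower, is at 0.11^0.661 = 0.232 (distance 0.018) or 0.174^0.661 = 0.315 (distance 0.065). The orderings tie in likelihood because all data are at Combination 8, so the tie is broken at random. Under each of the five, rule 2a selects Combination 5.

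**What cannot be computed.** Section 4.3.2 gives single-agent frequencies for mucosal inflammation (37%) and stomatitis (36%) regardless of causality, without separating grade 3 or higher and without a split by leucovorin use. No difference in DLT rate, and so no shift in the MTD, follows from them.

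**The case against.** The strongest reply is that only one sentence is out of line. Tables 7 and 8 list leucovorin for both pralatrexate arms, section 5.2 names 5.2.1 to 5.2.3 as the place for administration details, and the 6.2 sentence can be read as covering rescue use alone. Most of that stands: section 6.2 as a whole is not conditional, and a site could well follow 5.2.2 throughout. It does not remove the conflict, because the sentence sits where the universal instruction should be and defines no separate regimen.

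A reader might also count 7.3.2 and 7.8.1 as further contradictions. They are not. In 7.3.2 the words "can be given at the treating physician" belong to a sentence that first affirms leucovorin with treatment as already described and then adds discretion for mucositis related to pralatrexate. In 7.8.1 the thrombocytopenia item says "Prophylactic folic acid and vitamin B12 supplements may be necessary to reduce hematologic toxicity", and the oral mucositis item omits leucovorin, but both refer back to 5.2.2.

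The dose calculation shows only that a design with cohorts of one reacts to one DLT, whatever its cause. That is correct. A reader might infer that the MTD is already biased, or that response rates are affected; nothing in the protocol shows that any participant went without leucovorin or what the effect would be. The Arm A example may also be moot. Section 7.6 opens Arm B only after Arms A and C complete enrollment, and Arm B already has 4 participants, although 10.4 still plans 5 more in Arm A. The Arm B example does not depend on this: up to 26 further participants are planned there.

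Finally, 5.2.2 and 6.2 both print "folic acid at the dose of 1,000 mg orally daily". A reader might call this an error of unit. The two places agree, and judging the figure would need the package insert, which is not at hand. It is at most a query.

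**Conclusion.** The contradiction between 5.2.2 with Tables 7-8 and the text of 6.2 is real and should be corrected. It leaves room for different cycle 1 prophylaxis against a toxicity that counts as a DLT and, in Arm B, directs pralatrexate de-escalation. One mucositis DLT more or less changes the next assignment by one pralatrexate step in either arm: Level 1 to Level -1, or Combination 8 to Combination 5. These results assume that the DLT counts stated in 10.1 are current and that the next participant is treated at the stated level.

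The conclusion goes no further. That sites have differed is a possibility, not a documented fact, and the effect on the MTD, the RP2D or the response rate cannot be sized from the protocol. No view is taken on which leucovorin rule is right.

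**What to change.** Reconcile the leucovorin sentence in 6.2 with 5.2.2 and Tables 7-8, so that one cycle 1 rule, chosen by the sponsor, applies to all pralatrexate recipients. State in Table 7 which section its reference points to. Align the wording of 7.3.2 and 7.8.1 with that rule, although neither contradicts it independently.

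Report cycle 1 leucovorin use next to the DLTs for each participant on pralatrexate, and name the co-medication in the RP2D statement. Section 7.7.1 already requires all concomitant medication on the CRF, so no new form is needed. In the same amendment the sponsor can check the folic acid figure and unit against the insert that both sections cite.

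The cost is a wording amendment and one listing, with no extra participants or visits. The one burden is checking leucovorin exposure for the 5 Arm A and 4 Arm B participants already counted in 10.1.

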### **5.2.3 Decitabine**

In Arm B, decitabine will be administered at the entry dose of  $10 \text{ mg/m}^2$  day 1 to day 5 (day 1 -> day 5) Q4W and de-escalated (if applicable) following the study design described in the Statistical Considerations.

In Arm C, decitabine will be administered at the entry dose of  $20 \text{ mg/m}^2$  day 1 to day 5 (day 1 -> day 5) Q4W and allocation of participants to doses of decitabine will be conducted according to the study design outlined in the Statistical Considerations.

For any additional information refer to FDA-approved package insert.

## **5.3 Dose Limiting Toxicities**

A dose limiting toxicity (DLT) is defined as any toxicity that occurs that is considered at least “possibly related to the study drug administration”. Only DLT’s that occur prior to initiation of cycle 2 will be used to determine dose escalation/de-escalation decisions.

DLT criteria are defined as follows:

1. Any non-hematologic toxicity greater and/or equal to grade 3, except for:
  - Alopecia
  - Untreated nausea or vomiting;
  - Untreated constipation or diarrhea;
  - Untreated dehydration or fatigue uncontrolled;
  - Any liver function test including AST/ALT, GGT, Alkaline phosphatase elevation that has returned to grade 1 or baseline by day1 of cycle 2;
2. Grade 4 neutropenia lasting more than 5 days despite GCS-F support;
3. Febrile neutropenia (ANC <  $1000/\text{mm}^3$  with a single temperature of  $> 38.3^\circ\text{C}$  or sustained temperature of  $\geq 38^\circ\text{C}$  for over one hour);
4. Any grade 4 thrombocytopenia or grade 3 thrombocytopenia with clinically significant bleeding or any grade-3 thrombocytopenia requiring platelet transfusion
5. Grade 4 anemia unexplained by underlying disease involvement;

6. Failure to meet the required blood parameters for cycle 2 day 1.

Management and dose modifications associated with adverse events will be described in the following sections 7.0, 7.1, 7.2 (Dose selection, dose delays, dose modification).

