### **Safety**

The most frequent AEs, regardless of causality, reported in single-agent studies of hematologic malignancies were fatigue (n=86, 47%), nausea (n=74, 41%), mucosal inflammation (n=67, 37%), stomatitis (n=66, 36%), and constipation (n=65, 36%).

Patients with ATLL and HTLV-1 will be closely monitored by both the principle investigator and the DSMB.

Patients receiving pralatrexate should be monitored closely because AEs may occur at any time during therapy. For detailed information about the safety profile of pralatrexate, refer to the current pralatrexate IB and/or package insert.

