#### **5.4 Required Blood Parameters and Other Investigations Prior to Each Treatment**

Before the start of each cycle, patients should be reassessed, and the following criteria must be fulfilled:

- Absolute neutrophil count (ANC)  $> 1000/\mu\text{L}$
- Platelet count  $\geq 50,000/\mu\text{L}$
- Serum creatinine concentration  $\leq 2.0 \times$  institutional ULN or  $\leq$  baseline, or creatinine clearance  $> 50 \text{ ml/min}$  or baseline
- AST and ALT  $\leq 2.0 \times$  ULN or  $\leq 3.0 \times$  institutional ULN or baseline in presence of demonstrable lymphoma involvement of liver
- Bilirubin concentration  $\leq 1.5 \times$  ULN or direct bilirubin  $\leq$  ULN for patients with total bilirubin levels  $> 1.5 \times$  ULN
- Recovery of any drug-related non-hematological AE to grade  $\leq 1$ , unless otherwise indicated
- The above blood parameters are required to start day 1 treatment of every cycle with decitabine but do not need to be evaluated on day 2, day 3, day 4 and day 5 of each cycle unless clinically indicated.

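### DLT criterion 1 in section 5.3 exempts uncontrolled but not controlled fatigue of grade 3 or more, and its exceptions for untreated events have no definition and no grade limit

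*Protocol*

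**What the plan says.** Protocol section 5.3, criterion 1, reads "Any non-hematologic toxicity greater and/or equal to grade 3, except for" and then lists alopecia, "Untreated nausea or vomiting", "Untreated constipation or diarrhea", "Untreated dehydration or fatigue uncontrolled", and liver-test elevations that have recovered by day 1 of cycle 2. Only the liver-test item carries a recovery condition. The nausea, bowel, dehydration and fatigue items have no grade cap and no duration, and neither *untreated* nor *uncontrolled* is defined.

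Other sections bear on the same events:

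- Criterion 6 of 5.3 adds "Failure to meet the required blood parameters for cycle 2 day 1". Section 5.4, to which it points, includes "Recovery of any drug-related non-hematological AE to grade" 1 or lower.
- Section 7.8.1 says "Diarrhea should be treated promptly as it could represent an immune-related adverse event due to pembrolizumab administration", and asks for aggressive treatment of nausea and vomiting.
- Table 10 permanently stops treatment for immune-related diarrhea or colitis at grade 4 or recurrent grade 3.
- Section 9.2.1.2 requires a DLT before cycle 2 to be reported on its own form within 24 hours of the site learning of it.

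These DLTs feed the dose-allocation models in 10.2 (target 25%, cohorts of one) and the safety bounds in 10.3.

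**The concern.** The DLT is the primary endpoint on which the MTD rests, so the definition must sort events the same way at every site and must not rank a worse event as the milder one. The fatigue phrase, taken as written, does rank it that way. The untreated exceptions make DLT status depend on what the site had done, and by when, rather than on what happened to the patient. Every event is untreated at onset, and the Protocol does not say at what moment the question is asked. Two sites could classify the same grade 4 diarrhea differently.

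The events concerned are not rare in kind. Section 4.3.2 gives fatigue in 47% and nausea in 41% of patients on single-agent pralatrexate, at any grade. With 10 patients per arm in Arms A and C and a decision after each one, a single classification can change the dose.

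**Working it through.** **1. What the text does, case by case** (related event, grade 3 or more, before cycle 2)

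| Event | Status under criterion 1 as printed |
|---|---|
| Fatigue, uncontrolled | Exempt |
| Fatigue, controlled | DLT |
| Nausea, vomiting, constipation, diarrhea or dehydration, untreated | Exempt, including grade 4 |
| The same events, treated and persisting | DLT |
| The same events, treated and resolved | DLT |

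The reversal is confined to the first two rows. In the last three rows the order is sensible, but the line between them rests on an undefined word.

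**2. Is there a backstop?** Criterion 6 could catch an event still above grade 1 at cycle 2 day 1 through the recovery item in 5.4. But criterion 6 names blood parameters only, and the heading of 5.4 separates blood parameters from other investigations. A severe event that resolves before cycle 2 escapes in either case.

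**3. One patient in Arm A.** Inputs from 10.1 to 10.3: skeleton 0.25 at Level 1 (called dose level 3 in 10.5), 0.15 at Level -1 and 0.08 at Level -2; 1 DLT in 5 so far, all at Level 1; the arm stops when the recommended level already has 7 patients. With all data at one level, the maximum-likelihood fit there equals y/n. So exp(a) = ln(y/n)/ln(0.25), and the fitted rate at Level -1 is 0.15^exp(a).

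| Data at Level 1 | exp(a) | Level 1 | Level -1 | Distance from 0.25 | Recommended |
|---|---|---|---|---|---|
| 2/6 (event counted) | 0.792 | 0.333 | 0.222 | 0.083 v 0.028 | Level -1 |
| 1/6 (event exempt) | 1.292 | 0.167 | 0.086 | 0.083 v 0.164 | Level 1 |
| 1/7 (exempt, then no DLT) | 1.404 | 0.143 | 0.070 | 0.107 v 0.180 | Level 1 |
| 2/7 (exempt, then a DLT) | 0.904 | 0.286 | 0.180 | 0.036 v 0.070 | Level 1 |

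At 2/6, Level -2 is fitted at 0.08^0.792 = 0.135, which is further from target. If the sixth patient's event is exempt, Level 1 has 7 patients after the next one and is declared the MTD whichever way that patient goes. If it is counted, the next patient goes to Level -1.

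**4. Arm B.** Section 10.1 reports 1 DLT in 4 at Combination 8, whose skeleton value is 0.25 in every ordering. The next event gives 2/5 = 0.40 if counted and 1/5 = 0.20 if exempt. At 0.40, exp(θ) = ln(0.40)/ln(0.25) = 0.661, and lower combinations with skeleton 0.174 or 0.110 are fitted at 0.315 or 0.233, both nearer 25%. I stop there, because the allocation rule after a DLT in 10.2 names only mucositis, neutropenia and thrombocytopenia.

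**5. Sensitivity range, on assumed losses only.** The Arm A table in 10.5 gives selection of the top level as 71.7%, 44.7% and 23.5% in scenarios 1 to 3. A simulation of the 10.2 model (5,000 trials, 10 patients, without the stop at 7) gives 72.6%, 46.4% and 22.2%, so the printed figures are reproduced within 2 points. Now assume a share m of true DLTs is lost through the exceptions, so that observed rate = true rate × (1 − m).

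| Top level selected | m = 0 | 10% | 20% | 30% | 40% |
|---|---|---|---|---|---|
| Scenario 2 (true rate 0.40 there) | 46.4% | 53.9% | 60.5% | 67.5% | 74.3% |
| Scenario 3 (true rate 0.55 there) | 22.2% | 30.1% | 39.0% | 48.5% | 58.5% |

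The Protocol supplies no value of m. The m = 0 column means that every such event counts, which is a reference point and not the proposed fix.

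**The case against.** For the gastrointestinal events and dehydration, leaving out toxicity that has had no supportive care is a coherent exception. Treated events still count, and 7.8.1 expects treatment, so few events should qualify. Immune-related grade 4 diarrhea handled under Table 10 receives corticosteroids and would then be treated, hence a DLT. The fatigue phrase may be a drafting slip, and *untreated* may have been meant to govern fatigue as well.

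Most of this stands, and it limits the point. A reader might infer that the worse event is a non-DLT throughout the list; the text supports that for fatigue only. What survives is that *untreated* has no time reference, that the form is due within 24 hours, and that nothing in 5.3 says an event ending treatment must be a DLT. On the second parsing of the fatigue phrase, *uncontrolled* still has no clear job.

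A reader might also infer that the MTD is biased upward. The direction is conditional on events actually being exempted. For fatigue, the literal text also makes controlled grade 3 or higher fatigue a DLT, so against a rule that exempted controlled and counted uncontrolled fatigue the net effect could go either way.

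Another calculation subtracts 5, 10 or 15 points from every level's rate and applies the stop at 7. The scenario 2 top level is then declared the MTD in 83.2%, 87.8% or 91.9% of trials, against 78.0% with no loss. Those figures should not be read as the size of this defect. The losses are assumed, and most of the 78.0% comes from the stop at 7, since the printed table shows 44.7%.

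Finally, 7.6 opens Arm B only after Arms A and C are complete, and 10.1 already reports Arm B patients, so Arm A may be closed in practice. Section 10.4 still plans 5 more patients there. The wording applies equally to Arm B, where up to 26 more are planned.

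**Conclusion.** The point holds in limited form. The fatigue exception as printed reverses severity in the primary endpoint. The untreated exceptions do not, but they are undefined and uncapped, and they sit uneasily with Table 10 and 7.8.1. Criterion 6 is at best an uncertain backstop.

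The one result that needs no assumed event rate is the single-patient one: a sixth Arm A patient with such an event sends the next patient to Level -1 if it is counted, or keeps Level 1 if it is exempt. Beyond that, exempting events lowers the observed DLT rate and moves the model upward by an amount the documents cannot fix. If 10% to 40% of true DLTs were lost, selection of the top level would rise by about 7 to 28 points in scenario 2 and 8 to 36 points in scenario 3. This is a sensitivity range, not an estimate. The wording should be corrected before further accrual.

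**What to change.** In 5.3, criterion 1:

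- Correct the fatigue wording so that the exception does not cover the worse event.
- State what *untreated* means, including the moment at which it is judged.
- Reconcile the exceptions with 5.4, Table 10 and 7.8.1, and say whether an event that forces permanent discontinuation can be a non-DLT. Table 10 and 7.8.2 also differ on a first grade 3 diarrhea, so that must be settled in the same pass.
- Say whether criterion 6 covers the non-hematologic recovery item in 5.4.

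Grade and time limits are for the clinical leads. One caution on drafting: an exception defined by recovery under supportive care would newly exempt treated events that count as DLTs today. It should be adopted only if that is intended.

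Add a field to the DLT form for whether and when supportive care was given, and state whether DLT calls already made stand under the clarified wording.

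The cost is one reworded list, a few cross-references and one form field. Whether the DLT count rises or falls depends on the limits chosen.
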